3.7 Treatment of Infusion Reactions

In case of hypersensitivity reactions, the investigator should institute treatment measures deemed medically appropriate in accordance with current medical practice and treatment guidelines. Prophylactic premedication will not be routinely given before the first dose of Cycle 1. Prophylactic medication to prevent future infusion reactions may be considered after discussion and agreement between investigator(s) and Sponsor/medical monitor. Infusion reactions should be graded according to NCI CTCAE v4.03 guidelines and recorded in the CRF. Treatment recommendations are provided and may be modified based on local treatment standards and guidelines, as appropriate: In the case of infusion reactions during nivolumab administration, subsequent infusion times for individual subjects may be extended at the discretion of the investigator.

For Grade 1 symptoms (mild reaction; infusion interruption not indicated; intervention not indicated):

- Remain at bedside and monitor subject until recovery from symptoms.
- The following prophylactic premedications are recommended for future infusions: diphenhydramine 50 mg (or equivalent) and/or acetaminophen/paracetamol 325 to 1000 mg at least 30 minutes before additional study drug administrations.

For Grade 2 symptoms (moderate reaction; requires therapy or infusion interruption but responds promptly to symptomatic treatment [eg, antihistamines, nonsteroidal anti-inflammatory drugs, narcotics, corticosteroids, IV fluids]; prophylactic medications indicated for < 24 hours):

- Stop the study drug infusion, begin an IV infusion of normal saline, and treat the subject with diphenhydramine 50 mg IV (or equivalent) and/or acetaminophen/paracetamol 325 to 1000 mg; remain at bedside and monitor subject until resolution of symptoms. Corticosteroid therapy and/or bronchodilator may also be administered as appropriate.
- If infusion is interrupted, then restart the infusion at 50% of the original infusion rate when symptoms resolve; if no further complications ensue after 30 minutes, the rate may be increased to 100% of the original infusion rate. Monitor subject closely.
- If symptoms recur, then no further study drugs will be administered at that visit.
- The amount of study drug infused must be recorded on the CRF.

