- The following prophylactic premedications are recommended for future infusions: diphenhydramine 50 mg (or equivalent), acetaminophen/paracetamol 325 to 1000 mg, and/or corticosteroids (up to 25 mg of hydrocortisone or equivalent) should be administered at least 30 minutes before additional study drug administrations. Remain at bedside and monitor subject until recovery from symptoms.

For Grade 3 or Grade 4 symptoms (Grade 3: severe reaction; prolonged [ie, not rapidly responsive to symptomatic medication and/or brief interruption of infusion]; recurrence of symptoms following initial improvement; hospitalization indicated for other clinical sequelae [eg, renal impairment, pulmonary infiltrates]. Grade 4: life threatening; pressor or ventilatory support indicated):

- Immediately discontinue infusion of all study drugs.
- Begin an IV infusion of normal saline and treat the subject as follows: Recommend bronchodilators, epinephrine 0.2 to 1 mg of a 1:1,000 solution for subcutaneous administration, 0.3 mg of a 1:1,000 solution for intramuscular administration, or 0.1 to 0.25 mg of a 1:10,000 solution slowly for IV administration, and/or diphenhydramine 50 mg IV (or equivalent) with methylprednisolone 100 mg IV (or equivalent), as needed.
- Subject should be monitored until the investigator is comfortable that the symptoms will not recur. All study drugs will be permanently discontinued.
- The amount of study drug infused must be recorded on the CRF.
- For Grade 3 infusion reactions that resolve within 6 hours, the following prophylactic premedications are recommended for future infusions: diphenhydramine 50 mg (or equivalent), acetaminophen/paracetamol 325 to 1000 mg, and/or corticosteroids (up to 25 mg of hydrocortisone or equivalent) should be administered at least 30 minutes before additional

study drug administrations. Remain at bedside and monitor subject until recovery from symptoms.

- For Grade 3 infusion reaction that does not resolve in 6 hours and Grade 4 infusion reactions, study drug will be permanently discontinued.
- Investigators should follow their institutional guidelines for the treatment of anaphylaxis.
- Remain at bedside and monitor subject until recovery from symptoms.
- In the case of late-occurring hypersensitivity symptoms (eg, appearance of a localized or generalized pruritus within 1 week after treatment), symptomatic treatment may be given (eg, oral antihistamine or corticosteroids).

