All Grade 3 or 4 infusion reactions should be reported within 24 hours to the BMS Medical Monitor and reported as an SAE if criteria are met. Additional samples for PK and immunogenicity assessments, referred to as "Grade 3+ Infusion Reaction Event" samples, will be drawn in cases of Grade 3 to 4 infusion or hypersensitivity reactions (see Section 5.5.1).

If a subject discontinues treatment for an AE, both study drugs should be stopped. If there is an infusion reaction with only 1 study drug and it resolves quickly and is low grade, then the subject can continue both study drugs.

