4.3.1 BMS-986183

There will be no individual subject dose escalations of BMS-986183 allowed. Subjects should be carefully monitored for infusion reactions during BMS-986183 administration. If an infusion reaction is noted, subjects should be managed according to the guidance provided in Section 3.7.

Doses of BMS-986183 may be interrupted, delayed, or discontinued as described in Sections 3.7 and 4.5.

BMS-986183 Preparation:

BMS-986183 is supplied as a sterile, nonpyrogenic, single-use, preservative-free, lyophilized cake. Study drug is supplied as 50 mg/vial that must be reconstituted and diluted prior to dosing the subjects as an IV injection formulation. A sufficient excess of BMS-986183-01 is incorporated into each vial to account for withdrawal losses.

Solution for infusion is prepared by reconstituting BMS-986183-01 followed by further dilution to concentrations appropriate for the dosing cohort.

Prepared BMS-986183-01 infusion is administered to subjects as IV infusion.

BMS-986183 Administration:

Appropriate volume of prepared BMS-986183-01 solution should be administration through IV infusion set (using sterile, nonpyrogenic, low protein binding, polyethersulfone 0.2- μ m in-line filter - [supplied by the site]). Care must be taken to ensure the sterility of the prepared solution, as the drug product does not contain antimicrobial preservatives or bacteriostatic agents. Equilibration to room temperature is recommended for the drug product, infusion fluid, and their combination prior to administration.

Final diluted solutions of BMS-986183-01 for injection is stable for up to 24 hours at refrigerated conditions (2° to 8°C [36° to 46°F]) and protected from light (diluted solution may also be stored at room temperature conditions, 15 to 25°C [59° to 77°F] under ambient light for a total of up to 4 hours out of the total 24 hour storage period). The constituted vial and diluted bag should not be shaken. Equilibration to room temperature is recommended for drug product infusion fluid and their combination prior to administration. Infusion of BMS-986183-01 injection must be completed within 24 hours of dilution. The start of drug infusion equals 0 hour.

Detailed instructions for drug product preparation, administration, and storage are provided in separate dosing instruction manual.

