4.3.2 Nivolumab

Subjects should receive nivolumab at a dose of 360 mg as a 30-minute infusion on Day 1 of each treatment cycle until progression, unacceptable toxicity, withdrawal of consent, or the study ends, whichever occurs first.

For combination treatment in BMS-986183 and nivolumab dose escalation (Part 3) and BMS-986183 and nivolumab dose expansion (Part 4), BMS-986183 will be administered as an infusion for up to 60 minutes. The infusion line containing BMS-986183 should be flushed with an appropriate amount of diluent to ensure that the entire dose is administered and that the infusion line is cleared of any remaining BMS-986183. The nivolumab dose would then be infused not less than 30 minutes from the completion of the BMS-986183 infusion, which would then be infused over a period of 30 minutes.

There will be no individual subject dose escalations or reductions of nivolumab allowed. Subjects may be dosed no less than 18 days from the previous dose during Q3W cycles. For Q3W dosing cycles, subjects may be dosed within $a \pm 3$ -day window. Premedications are not recommended for the first dose of nivolumab.

Subjects should be carefully monitored for infusion reactions during nivolumab administration. If an infusion reaction is noted, subjects should be managed according to Section 4.5.2.2.

Doses of nivolumab may be interrupted, delayed, or discontinued depending on how well the subject tolerates the treatment.

Nivolumab Injection, 100 mg/10 mL (10 mg/mL) is to be administered as an IV infusion through a 0.2- to 1.2-micron pore size, low-protein binding in-line filter at the protocol-specified doses. It is not to be administered as an IV push or bolus injection. Nivolumab Injection can be infused undiluted (10 mg/mL) or diluted with 0.9% Sodium Chloride Injection, USP or 5% Dextrose Injection, USP to protein concentrations as low as 1 mg/mL. Instructions for dilution and infusion of Nivolumab Injection may be provided in the pharmacy manual. Care must be taken to assure sterility of the prepared solution because the product does not contain any antimicrobial preservative or bacteriostatic agent.

Nivolumab infusions are compatible with polyvinyl chloride (or polyolefin containers and infusion sets) and glass bottles.

Separate infusion bags and filters should be used when administering nivolumab and BMS-986183 on the same day.

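### After a drug-related Grade 3 infusion reaction that clears in under 6 hours, Protocol 3.7 and 4.5.6 each give both a stop instruction and a route to re-dosing, with no order of precedence

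*Protocol*

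**What the plan says.** Protocol 3.7 treats Grade 3 and Grade 4 infusion reactions under one joint heading. Three items in that list bear on the point:

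- An unqualified stop: "All study drugs will be permanently discontinued".
- A plan for continuing: "For Grade 3 infusion reactions that resolve within 6 hours, the following prophylactic premedications are recommended for future infusions".
- A stop limited by time and grade: "For Grade 3 infusion reaction that does not resolve in 6 hours and Grade 4 infusion reactions, study drug will be permanently discontinued".

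The opening paragraph of 3.7 describes its content as treatment recommendations that local standards may modify. It adds: "Prophylactic medication to prevent future infusion reactions may be considered after discussion and agreement between investigator(s) and Sponsor/medical monitor". The section closes with a reporting duty: "All Grade 3 or 4 infusion reactions should be reported within 24 hours to the BMS Medical Monitor".

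Protocol 4.5.6 lists criteria for which permanent discontinuation is required, and 4.5.4 repeats that subjects meeting them must stop. One bullet names a drug-related Grade 3 infusion reaction, whatever its duration. A separate bullet covers Grade 3 or 4 events that meet the DLT criteria and lets investigator and Medical Monitor agree exceptions. The first exception listed is a Grade 3 infusion reaction that is back at Grade 1 in under 6 hours. The section ends with a general provision for a benefit/risk discussion with the Medical Monitor.

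Protocol 4.5.1 names that same short-lived reaction among the Grade 3 or higher nonhematologic events that are not DLTs.

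**The concern.** Whether a subject may be given the drug again after a severe infusion reaction should have one answer. Here an investigator who re-doses under the 6-hour provision departs from the blanket sentence in 3.7 and from the mandatory bullet in 4.5.6. An investigator who stops departs from the 6-hour provision and may withdraw treatment from a subject with advanced hepatocellular carcinoma whom the protocol apparently meant to keep on study. A Medical Monitor who is consulted has no unambiguous default to apply. According to Protocol 1.4.4 the trial is first-in-human for BMS-986183, so there is no clinical experience to fall back on.

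**Working it through.** No arithmetic applies. The check is whether the provisions can all hold for one event: a first drug-related Grade 3 infusion reaction that returns to Grade 1 in under 6 hours.

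| Place | Instruction for this event | Condition attached |
|---|---|---|
| 3.7, blanket sentence | Stop all study drugs permanently | None |
| 3.7, 6-hour bullets | Premedicate and continue; stop only for Grade 4, or Grade 3 not resolved in 6 hours | None in the bullets; sponsor agreement on prophylaxis in the opening paragraph |
| 4.5.6, Grade 3 bullet | Stop permanently | Drug-related; duration irrelevant |
| 4.5.6, exception list | May continue | Medical Monitor consultation; placed under events meeting DLT criteria |

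**Step 1, within 3.7.** The first two rows cannot both be followed. The later, more specific bullets can be read as narrowing the blanket sentence. If so, that sentence adds nothing, because the last bullet already states when to stop.

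**Step 2, within 4.5.6.** The exception is attached to the DLT bullet and not to the Grade 3 bullet that imposes the stop. To qualify under its own heading, the event must first be a DLT, and 4.5.1 generally says it is not. On its wording, the exception therefore does not clearly release a first short-lived reaction from the other bullet.

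**Step 3, between the sections.** Even if 3.7 is read as a pure 6-hour rule, it conflicts with a bullet in 4.5.6 that makes duration irrelevant. Neither section says which prevails.

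**Step 4, other places that might settle it.** All of them lead back to 3.7:

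- Section 4.3.1: "If an infusion reaction is noted, subjects should be managed according to the guidance provided in Section 3.7".
- Section 4.3.2: "If an infusion reaction is noted, subjects should be managed according to Section 4.5.2.2". That section in turn sends the reader to 3.7.
- The infusion-reaction row of Table 4.5.2-1 gives no action and only cites 3.7.
- The SAP contains no re-exposure rule.

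**The case against.** The strongest reply is that the texts combine into a sensible whole. On this reading the default is to stop. A Grade 3 reaction clearing in under 6 hours may continue with premedication after Medical Monitor consultation, and other Grade 3 and all Grade 4 reactions stop. The mandatory criteria of 4.5.6 include their own exceptions, and 3.7 offers recommendations. This is very probably what was meant. As a reading of the text, however, it needs both the blanket sentence in 3.7 and the duration clause in 4.5.6 to be set aside, and nothing instructs the reader to do that. The benefit/risk provision at the end of 4.5.6 permits an override but does not state the default.

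The reply does succeed against several stronger readings that a reader might infer:

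- *That the 4.5.6 exception can never apply.* Section 4.5.1 makes recurrent Grade 3 or higher infusion reactions a DLT in their own bullet, separate from the one carrying the exclusions. A recurrent short-lived reaction could meet DLT criteria, which gives the exception a literal use.
- *That the end of 3.7 forbids continuing after Grade 3.* For a reaction to one drug only, it says that if "it resolves quickly and is low grade, then the subject can continue both study drugs". That is a sufficient condition for continuing. It does not address a short-lived Grade 3 reaction.
- *That the recurrence DLT proves re-dosing was intended.* Recurrence may occur within one episode: 3.7 itself describes Grade 3 as including symptoms that return after initial improvement.
- *That sites would diverge unsupervised.* The 24-hour report, sponsor agreement on prophylaxis and the Medical Monitor's role in 4.5.6 make that unlikely.

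**Conclusion.** The point stands as an internal inconsistency in a mandatory stopping rule, and it should be corrected. It concerns one event, the drug-related Grade 3 infusion reaction that clears in under 6 hours. The rules for Grade 4 and for longer Grade 3 reactions agree. The documents give no frequency for the event, so no count of affected subjects is offered.

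Practical risk is limited by the oversight already in place. A reader might infer damage to the primary endpoint of adverse events leading to discontinuation, but the documents do not support more than a minor effect. SAP 7.5 classifies such events by the action actually recorded, and the protocol tests no formal hypothesis.

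The conclusion rests on the wording of 3.7, 4.5.1, 4.5.4 and 4.5.6. The direction of the fix rests on one further judgement, that the 6-hour rule with Medical Monitor consultation is what the sponsor intended. If the sponsor prefers to stop after every Grade 3 reaction, the re-dosing text should be deleted instead; either choice removes the conflict.

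**What to change.** Two changes are needed, by amendment:

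1. **Section 3.7.** Limit the sentence "All study drugs will be permanently discontinued" to Grade 4 reactions and Grade 3 reactions not resolved in 6 hours. Alternatively, delete it, since the later bullet already covers those cases.
2. **Section 4.5.6.** Exempt from the Grade 3 bullet an infusion reaction that is back at Grade 1 in under 6 hours, and require Medical Monitor agreement before re-dosing. Attach the existing exception to that bullet, so that it no longer depends on the event being a DLT.

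Three further edits are optional: defining low grade in the closing paragraph of 3.7, stating whether the exemption extends to bronchospasm or hypersensitivity within the infusion reaction, and using one recovery wording in 3.7, 4.5.1 and 4.5.6.

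The cost is a few sentences. Sample size, visit schedule and analysis do not change.

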4 STUDY DRUG

Product description and storage information are described in Table 4-1.

Product Description Class and Dosage Form	Potency	IP/NonIMP	Blinded or Open Label	Packaging/Appearance	Storage Conditions (per label)
BMS-986183-01 for Injection	50 mg/vial	IP	Open label	Primary Packaging: Glass vial Secondary Packaging: Outer carton 10 cc vial/White to off- white, whole or fragmented cake in a vial Lyophilized	Protect from light Store at 2 to 8°C
Nivolumab Solution for Injection	100 mg/vial (10 mg/mL)	IP	Open label	Primary Packaging: 10 mL (10 cc) glass vial Secondary Packaging: Outer carton Appearance: Vial containing 10 mL clear to opalescent, colorless to pale yellow liquid, light (few) particulates may be present.	2°C to 8°C (36°F to 46°F). Protect from light. Protect from freezing.

Table 4-1:Study Drugs for CA015003

IMP = investigational medicinal product.

4.1 Investigational Product

An IP, also known as investigational medicinal product in some regions, is defined as a pharmaceutical form of an active substance or placebo being tested or used as a reference in a clinical study, including products already with a marketing authorization but used or assembled (formulated or packaged) differently than the authorized form, or used for an unauthorized indication, or when used to gain further information about the authorized form.

The IP should be stored in a secure area according to local regulations. It is the responsibility of the investigator to ensure that IP is only dispensed to study subjects. The IP must be dispensed only from official study sites by authorized personnel according to local regulations.

In this protocol, the IPs are BMS-986183-01 for injection, 50 mg/vial, and nivolumab for injection, 100 mg/vial.

4.2 Noninvestigational Product

Other medications used as support or escape medication for preventative, diagnostic, or therapeutic reasons, as components of the standard of care for a given diagnosis, may be considered as non-IPs. Not applicable for this study.

4.3 Storage and Dispensing

The product storage manager should ensure that the study drug is stored in accordance with the environmental conditions (temperature, light, and humidity) as determined by BMS. If concerns regarding the quality or appearance of the study drug arise, the study drug should not be dispensed and contact BMS immediately.

Study drug not supplied by BMS will be stored in accordance with the package insert.

IP documentation (whether supplied by BMS or not) must be maintained that includes all processes required to ensure drug is accurately administered. This includes documentation of drug storage, administration and, as applicable, storage temperatures, reconstitution, and use of required processes (eg, required diluents, administration sets).

4.3.1 BMS-986183

There will be no individual subject dose escalations of BMS-986183 allowed. Subjects should be carefully monitored for infusion reactions during BMS-986183 administration. If an infusion reaction is noted, subjects should be managed according to the guidance provided in Section 3.7.

Doses of BMS-986183 may be interrupted, delayed, or discontinued as described in Sections 3.7 and 4.5.

BMS-986183 Preparation:

BMS-986183 is supplied as a sterile, nonpyrogenic, single-use, preservative-free, lyophilized cake. Study drug is supplied as 50 mg/vial that must be reconstituted and diluted prior to dosing the subjects as an IV injection formulation. A sufficient excess of BMS-986183-01 is incorporated into each vial to account for withdrawal losses.

Solution for infusion is prepared by reconstituting BMS-986183-01 followed by further dilution to concentrations appropriate for the dosing cohort.

Prepared BMS-986183-01 infusion is administered to subjects as IV infusion.

BMS-986183 Administration:

Appropriate volume of prepared BMS-986183-01 solution should be administration through IV infusion set (using sterile, nonpyrogenic, low protein binding, polyethersulfone 0.2- μ m in-line filter - [supplied by the site]). Care must be taken to ensure the sterility of the prepared solution, as the drug product does not contain antimicrobial preservatives or bacteriostatic agents. Equilibration to room temperature is recommended for the drug product, infusion fluid, and their combination prior to administration.

Final diluted solutions of BMS-986183-01 for injection is stable for up to 24 hours at refrigerated conditions (2° to 8°C [36° to 46°F]) and protected from light (diluted solution may also be stored at room temperature conditions, 15 to 25°C [59° to 77°F] under ambient light for a total of up to 4 hours out of the total 24 hour storage period). The constituted vial and diluted bag should not be shaken. Equilibration to room temperature is recommended for drug product infusion fluid and their combination prior to administration. Infusion of BMS-986183-01 injection must be completed within 24 hours of dilution. The start of drug infusion equals 0 hour.

Detailed instructions for drug product preparation, administration, and storage are provided in separate dosing instruction manual.

4.3.2 Nivolumab

Subjects should receive nivolumab at a dose of 360 mg as a 30-minute infusion on Day 1 of each treatment cycle until progression, unacceptable toxicity, withdrawal of consent, or the study ends, whichever occurs first.

For combination treatment in BMS-986183 and nivolumab dose escalation (Part 3) and BMS-986183 and nivolumab dose expansion (Part 4), BMS-986183 will be administered as an infusion for up to 60 minutes. The infusion line containing BMS-986183 should be flushed with an appropriate amount of diluent to ensure that the entire dose is administered and that the infusion line is cleared of any remaining BMS-986183. The nivolumab dose would then be infused not less than 30 minutes from the completion of the BMS-986183 infusion, which would then be infused over a period of 30 minutes.

There will be no individual subject dose escalations or reductions of nivolumab allowed. Subjects may be dosed no less than 18 days from the previous dose during Q3W cycles. For Q3W dosing cycles, subjects may be dosed within $a \pm 3$ -day window. Premedications are not recommended for the first dose of nivolumab.

Subjects should be carefully monitored for infusion reactions during nivolumab administration. If an infusion reaction is noted, subjects should be managed according to Section 4.5.2.2.

Doses of nivolumab may be interrupted, delayed, or discontinued depending on how well the subject tolerates the treatment.

Nivolumab Injection, 100 mg/10 mL (10 mg/mL) is to be administered as an IV infusion through a 0.2- to 1.2-micron pore size, low-protein binding in-line filter at the protocol-specified doses. It is not to be administered as an IV push or bolus injection. Nivolumab Injection can be infused undiluted (10 mg/mL) or diluted with 0.9% Sodium Chloride Injection, USP or 5% Dextrose Injection, USP to protein concentrations as low as 1 mg/mL. Instructions for dilution and infusion of Nivolumab Injection may be provided in the pharmacy manual. Care must be taken to assure sterility of the prepared solution because the product does not contain any antimicrobial preservative or bacteriostatic agent.

Nivolumab infusions are compatible with polyvinyl chloride (or polyolefin containers and infusion sets) and glass bottles.

Separate infusion bags and filters should be used when administering nivolumab and BMS-986183 on the same day.

